**Assessments.** The instruments to be used were selected because many are standardized, have good psychometric properties, are widely used, and have been used by our research group. The primary outcome measures are described in this section. Information regarding additional measures can be found in Table 1.

Primary clinical outcomes include: the CAPS-5 for clinician-rated and PCL-5 for self-reported PTSD symptoms. The CAPS-5 is a 30-item structured diagnostic interview and gold standard for assessing PTSD (Weathers, Blake, et al., 2013). Independent evaluators blind to treatment condition will conduct the CAPS-5 at baseline, end of treatment, and follow up. The PCL-5 is a 20-item self-report measure that assesses PTSD severity each week and has excellent psychometric characteristics (Weathers, Litz, et al., 2013). IVE assessments include: psychophysiological reactivity (HR and GSR), which will be measured passively and continuously during IVEs using the patient worn data acquisition system (Zeriscope Inc.). Consistent with imaginal exposures, Subjective Units of Distress (SUDS; 0=no anxiety to 100=extreme anxiety) will be collected at 5-minute intervals during IVEs. A tone will signal patients to enter their SUDS using the device. Self-report questionnaires employed in our pilot feasibility study and other studies will assess comfort, acceptability, willingness to use, utility, and client satisfaction (Attikisson & Greenfield, 2004; Rizzo et al., 2010).

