**General Statistical Analyses.** All analyses will be performed on the intent-to-treat sample consisting of all randomized subjects. Baseline clinical and demographic characteristics will be collected and t-tests, chi-square tests, or their non-parametric equivalents will test for group differences, as appropriate, in SAS v9.4 (SAS Institute, Cary, NC, USA). Baseline characteristics that are associated with the primary outcome measures will be included as covariates in subsequent analyses. For all analyses, alpha will be set at 0.05. Urn randomization will be stratified by PTSD severity (CAP-5 total score at baseline). Based on our sample size and assuming 20% attrition (N=32), we have 80% power to detect a large effect (Cohen's  $d = 1.02$ ) for treatment outcome at a probability level of 0.05 for a two-tailed test (Cohen, 1988).

Hypothesis 1: IB-PE will be feasible and acceptable, as evidenced by at least 80% of participants (a) being able to turn on/off the equipment in  $\leq 5$  minutes; (b) reporting positive perceptions toward IB-PE via self-report assessments (Sekhon, Cartwright, & Francis, 2017). Hypothesis 2: Participants in the IB-PE guided group will evidence significantly greater pre- to post-treatment reductions in PTSD severity as compared to the record-only group. To test this hypothesis, independent generalized linear mixed effects models will be used to examine PCL-5 and CAPS-5 scores at final session by group. Models will be adjusted, respectively, for baseline PCL-5 and CAPS-5. Group will be entered as the predictor variable. Hypothesis 3: Higher levels of physiological and subjective engagement will predict greater treatment response. To test this hypothesis, mean HR, GSR, and SUDS responses during IVEs will be calculated according to previously published methods (Norholm et al., 2016; Rauch et al., 2018; Rothbaum et al., 2014) and multilevel modeling (MLM) will be used to analyze these variables as predictors of CAPS-5 at final session within and between treatment groups.

Exploratory analyses will examine group differences in the number of sessions required to attain significant symptom improvement on the PCL-5 from baseline (Rothbaum et al., 2014) and durability of effects at 1-month follow up. Data from both groups will be harnessed to explore the development of patient-specific algorithms predicting optimal engagement during IVE.

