**Follow-Up Phase.** All participants will be provided with a list of community resources upon study completion. Individuals presenting at any time with serious mental or physical health symptoms will be referred clinically for treatment. In the unlikely event that a participant demonstrates clinical deterioration, he/she will be referred clinically consistent with the procedures outlined in the Human Subjects section. In the event that emergency evaluation or intervention is necessary, the participant will be escorted by a study staff member to the psychiatric walk-in clinic or emergency room. Psychiatric hospitalization is available for emergencies at any point in the study.

**Data Management and Analysis.** A data analytic plan is outlined in the Statistical Analysis section. This study is powered to examine the efficacy of intelligent biometrics to optimize PE on the primary outcomes of interest. The main outcome variables include the severity of self-report and clinician-rated PTSD measures. Analyses will be guided by the specific hypotheses of the study and conducted by the study biostatistician. Post-hoc exploratory analyses will be conducted with two-tailed tests and more conservative statistical procedures which guard against Type I error (e.g., Tukey tests). All primary hypotheses will be tested at level of significance  $\alpha=0.05$ . We will also estimate the effect sizes of interest and provide 95% confidence intervals. Please see the Statistical Analysis and Power section for more details.

**Quality Assurance and Confidentiality.** Data quality will be monitored by random inspection of the completed forms by research staff and any irregularities or problems detected will be discussed with the PI. Project therapists will receive standardized training from the PI and Co-Is. Adherence to the manual will be monitored using session checklists and weekly supervision. If therapy drift is observed the therapists will be re-trained.

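### CAPS-5 and PCL-5 are joint, unranked primaries with no rule for confirming Hypothesis 2; if either suffices, false confirmation is about 3.5–4.9% instead of 2.5%

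*Combined protocol and SAP*

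**What the plan says.** Section 10.0 (Assessments) names two primaries side by side: "Primary clinical outcomes include: the CAPS-5 for clinician-rated and PCL-5 for self-reported PTSD symptoms". Section 4.0 and two paragraphs of section 13.0 (Summary of the Protocol; Data Management and Analysis) repeat the pairing, again without an order.

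Section 11.0 (General Statistical Analyses) states Hypothesis 2 once, for severity in general: "Participants in the IB-PE guided group will evidence significantly greater pre- to post-treatment reductions in PTSD severity as compared to the record-only group". It is then tested scale by scale: "independent generalized linear mixed effects models will be used to examine PCL-5 and CAPS-5 scores at final session by group". On covariates: "Models will be adjusted, respectively, for baseline PCL-5 and CAPS-5". On the significance level: "For all analyses, alpha will be set at 0.05". The power statement in the same section is for a two-tailed test of one treatment outcome.

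Section 13.0 applies 0.05 to all primary hypotheses and plans effect sizes with 95% confidence intervals. Its only multiplicity provision concerns other analyses: "Post-hoc exploratory analyses will be conducted with two-tailed tests and more conservative statistical procedures which guard against Type I error".

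**The concern.** One hypothesis is tested twice, and the plan does not say how the two results combine. When the scales agree, this does not matter. When only one is significant, the reader cannot tell whether Hypothesis 2 has been confirmed, and the choice could be made after the results are known.

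The scales are also not interchangeable. Under section 10.0, CAPS-5 is scored by independent evaluators who do not know the allocation. PCL-5 is completed by participants, who know whether a coach is leading their exposures. Without a rule, a significant PCL-5 could be reported as success while the blind-rated CAPS-5 is not significant.

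**Working it through.** **Inputs from the documents.** Two primary scales, unranked (sections 4.0, 10.0, 13.0). Alpha 0.05, two-tailed, for each test (section 11.0). 40 enrolled, 20% attrition, 32 analysed, 80% power at d = 1.02 (sections 6.0, 11.0). Allocation 3 guided to 1 record-only (section 3.0), so 24 and 8 of the 32.

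**Assumed.** The correlation rho between the scales is not given; 0 to 0.9 is used. The baseline-to-final correlation is set at 0.5. No reporting bias is built in.

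**Step 1: the plan's own figure.** For a two-sample t-test with 30 degrees of freedom, the noncentrality is d × √(n1·n2/(n1+n2)).
- 16 v 16: 1.02 × √8 = 2.885, power 79.7%. The stated 80% reproduces, for one test with equal arms.
- 24 v 8: 1.02 × √6 = 2.498, power 67.6%. The mismatch with 3:1 allocation is a separate point.

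**Step 2: the baseline for comparison.** Hypothesis 2 is directional and each test is two-sided at 0.05, so one test falsely confirms it with probability 0.05/2 = 0.025.

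**Step 3: either scale suffices.** With no true effect on either scale,

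P(either in the hypothesised direction) = 0.025 + 0.025 − P(both in that direction).

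At rho = 0, P(both) = 0.025² = 0.0006, giving 0.0494. At rho = 0.9, the bivariate normal gives P(both) = 0.0148, so 0.05 − 0.0148 = 0.0352.

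The planned adjustment was also simulated: each final score regressed on group and its own baseline, 24 v 8, 29 degrees of freedom, 1,000,000 trials per rho.

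| rho | Either, normal | Either, simulated | PCL-5 only, simulated | PCL-5-only share | Both, simulated |
|---|---|---|---|---|---|
| 0 | 4.94% | 4.91% | 2.44% | 50% | 0.06% |
| 0.5 | 4.54% | 4.56% | 2.06% | 45% | 0.42% |
| 0.7 | 4.17% | 4.22% | 1.73% | 41% | 0.78% |
| 0.8 | 3.90% | 3.98% | 1.50% | 38% | 1.02% |
| 0.9 | 3.52% | 3.56% | 1.07% | 30% | 1.42% |

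The share is PCL-5 only divided by either; at rho 0.9, 1.07/3.56 = 30%. The two methods differ by less than 0.1 percentage point.

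Counting significance in both directions, the simulated family-wise error runs from 9.7% (rho 0) to 7.1% (rho 0.9), against 5% for one test. That figure includes results favouring record-only, which could not confirm Hypothesis 2, so the directional figures are the relevant ones.

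**Step 4: both scales required.** If one scale has a large true effect and the other none, P(both) cannot exceed 0.025, the error of the null scale. With no effect on either, it is the last column. There is no inflation, but power drops: with d = 1.02 on both scales and equal arms of 16, joint power is about 68% (rho 0.5) to 75% (rho 0.9), not 80%.

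**Step 5: CAPS-5 first.** The false-confirmation rate is 2.5% whatever the correlation.

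**The case against.** The strongest reply is that the inflation depends on a rule the plan never states. Sections 4.0 and 11.0 join the scales with *and*, which is at least as compatible with requiring both. That is fair, and it is why the figures are conditional. But joint wording is not a decision rule, and requiring both would leave the stated power unmet.

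A second reply is that section 13.0 sets 0.05 per primary hypothesis, and the directional figure stays under 5% even at rho 0. It does, but a two-sided 0.05 test carries 2.5% in the hypothesised direction. On the two-sided count, two unadjusted tests exceed 0.05 for this hypothesis if either suffices.

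A third is that rho = 0 is implausible for two severity scales in the same people. That stands. At 0.7 to 0.9 the excess is 4.2 − 2.5 = 1.7 down to 3.6 − 2.5 = 1.1 percentage points, which is modest.

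The blinding contrast is also partial: CAPS-5 raters are blind, but the interview still depends on what unblinded participants report. And CAPS-5 is not measured between baseline and post-treatment, whereas PCL-5 is also collected at sessions 1–9. This adds little here, because Hypothesis 2 models both scales at the final session.

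Finally, the aim is preliminary efficacy in 40 people, and estimates with intervals are planned. This limits the consequence. Section 13.0 nevertheless describes the study as powered for efficacy on its primary outcomes, and Hypothesis 2 is worded in terms of significance.

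**Conclusion.** The concern holds. The plan gives two unranked primary outcomes for one hypothesis and no way to decide that hypothesis when they disagree. That gap does not depend on any assumed correlation.

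The size does. If either scale suffices, false confirmation is about 3.5% to 4.9% over rho 0.9 to 0, against 2.5%. If both are needed, the error is at most 2.5% but the stated 80% power is not delivered. Under either reading, a property the plan claims for itself is missed. The plan should be corrected, but in a small trial with a preliminary aim this does not undermine the design.

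**What to change.** In sections 4.0, 10.0 (Assessments), 11.0 (Hypothesis 2) and 13.0 (both paragraphs that list outcomes), name CAPS-5 at end of treatment as the single primary outcome for Hypothesis 2, tested at two-sided 0.05. Make PCL-5 the key secondary outcome, tested at two-sided 0.05 only if CAPS-5 is significant. Otherwise report it as an estimate with the 95% interval already planned.

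This order follows choices the plan has already made, although none of them ranks CAPS-5 first for Hypothesis 2. Section 10.0 calls CAPS-5 the gold standard and has it rated blind. Section 11.0 uses it for allocation: "Urn randomization will be stratified by PTSD severity (CAP-5 total score at baseline". It is also the only outcome for Hypothesis 3: "multilevel modeling (MLM) will be used to analyze these variables as predictors of CAPS-5 at final session within and between treatment groups".

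Requiring both scales or splitting alpha would also close the gap, at a price in power. Joint power is given in step 4. At two-sided 0.025 per scale, power for one scale at d = 1.02 is 69.9% with 16 v 16 and 56.0% with 24 v 8. Testing CAPS-5 first keeps its full 0.05.

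The change is wording only, with no added participants or visits. Its cost is that a significant PCL-5 with a non-significant CAPS-5 could no longer confirm Hypothesis 2.

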**Table 1. Assessment Instruments and Timeline**

Instrument Name	Purpose/Domain	BSL	Sessio n 1-9	Post TX	1 Mth F/U
Informed Consent	Obtain informed consent	X			
Demographics Form	Characterize sample	X			
MINI International Neuropsychiatric Interview	Assess DSM-5 psychiatric disorders	X			
Adverse Events	Monitor AEs and safety		X	X	X
Life Events Checklist: LEC	Assess trauma exposure	X			
Clinician Administered PTSD Scale: CAPS-5	PTSD symptom severity (clinician-rated)	X		X	X
C-SSRS	Assess suicidality	X		X	X
PTSD Checklist: PCL-5	PTSD symptom severity (self-report)	X	X	X	X
Beck Depression Inventory-II: BDI-II	Measure depression	X	X	X	X
Race Related Events Scale	Assess Race Related Trauma	X		X	X
Trauma Symptoms of Discrimination	Assess Race Related Trauma	X		X	X
Distress Tolerance Scale: DTS	Measure distress tolerance skills	X		X	X
Client Satisfaction Questionnaire-8: CSQ	Satisfaction with treatment			X	
Posttraumatic Cognitions Inventory PTCI	Assess trauma-related thoughts and beliefs	X	1, 5	X	X
COVID 19 Survey	Assess impact of COVID-19	X	5	X	X
Helping Alliance Questionnaire: HAQ-II	Assess therapeutic alliance			X	
Treatment Services Review: TSR	Monitor services utilization	X	5	X	X
In Vivo Exposures: IVEs	Assess biological and self-report indices of engagement (HR, GSR, SUDS), and evaluate feasibility and acceptability		3-9	X	
System Usability Scale: SUS	Assess usability and comfort		3,5	X	
SUS-Therapist	Assess usability and comfort		5	X	
Wangelin survey	Acceptability and comfort		3,5	X	
Turn on/off system in <5 min	Feasibility		2	X	
How often attempted to use and completed IVEs using the system	Feasibility		3,5	X	
Exit Feedback Survey	Collect general feedback on study treatment			X	

Note. BSL = baseline, TX = treatment, F/U = follow-up, HR = heart rate, GSR = galvanic skin response, SUDS = Subjective Units of Distress Scale

**Subject Compensation.** Subjects will receive \$50 for the baseline appointment, \$30 for each of the 10 visits and \$50 for the one-month follow up. The total compensation available is \$400. Payment will be provided in Visa gift card or pre-paid debit card, called a ClinCard. Subjects will be compensated at the end of each visit by IRB-approved study personnel.

The ClinCard works like a bank debit card and you may use the card to purchase goods or services everywhere Debit MasterCard is accepted as long as you do not exceed the balance available on the card. Participants will be given a ClinCard at the beginning of the study. Each

time they receive payment for participation in this study, the money will be added to the card, as outlined in the payment schedule above. The ClinCard will come with information on how to use the card, a phone number to call to set a PIN and a phone number to call to check the card balance as well as the study staff contact information in the case that the ClinCard is lost or stolen.

## 11.0 Data Management

**Overview.** Research materials obtained from participants include self-report surveys and structured clinical interviews, and physiological and behavioral observation data. All data collection described in this protocol is collected specifically for the purposes of the proposed research project. To maintain confidentiality, all digital and paper data collected will be numerically coded. Paper data will be kept in locked filing cabinets and digital files will be kept on password-protected computers within MUSC/RHJVA encrypted data server. No parties shall have access to these data aside from the PI and necessary research staff. A master list of participant names, study ID numbers, and contact information will be kept in a location separate from study materials within MUSC/RHJVA encrypted data server. VA data will be stored in dedicated research offices of the Study Coordinator and Research Assistant within the RHJVA Research Building. Access to research records (paper and computerized) will be restricted to the project staff. The data will be kept in a locked file cabinet within a locked office at the RHJVA. Names will not be used on specimens, assessments, or be available in the research laboratory. The investigators and all study personnel will sign a confidentiality agreement that no identifying information of specific individuals will appear in any internal reports or external documents (e.g., peer-reviewed publications, presentations). Research subjects' data will be entered in a computer database with only number codes for identifiers and will not identify study subjects by name. Custody and disposition of VA Federal Records are maintained in accordance with RCS 10-1

**General Statistical Analyses.** All analyses will be performed on the intent-to-treat sample consisting of all randomized subjects. Baseline clinical and demographic characteristics will be collected and t-tests, chi-square tests, or their non-parametric equivalents will test for group differences, as appropriate, in SAS v9.4 (SAS Institute, Cary, NC, USA). Baseline characteristics that are associated with the primary outcome measures will be included as covariates in subsequent analyses. For all analyses, alpha will be set at 0.05. Urn randomization will be stratified by PTSD severity (CAP-5 total score at baseline). Based on our sample size and assuming 20% attrition (N=32), we have 80% power to detect a large effect (Cohen's  $d = 1.02$ ) for treatment outcome at a probability level of 0.05 for a two-tailed test (Cohen, 1988).

Hypothesis 1: IB-PE will be feasible and acceptable, as evidenced by at least 80% of participants (a) being able to turn on/off the equipment in  $\leq 5$  minutes; (b) reporting positive perceptions toward IB-PE via self-report assessments (Sekhon, Cartwright, & Francis, 2017). Hypothesis 2: Participants in the IB-PE guided group will evidence significantly greater pre- to post-treatment reductions in PTSD severity as compared to the record-only group. To test this hypothesis, independent generalized linear mixed effects models will be used to examine PCL-5 and CAPS-5 scores at final session by group. Models will be adjusted, respectively, for baseline PCL-5 and CAPS-5. Group will be entered as the predictor variable. Hypothesis 3: Higher levels of physiological and subjective engagement will predict greater treatment response. To test this hypothesis, mean HR, GSR, and SUDS responses during IVEs will be calculated according to previously published methods (Norholm et al., 2016; Rauch et al., 2018; Rothbaum et al., 2014) and multilevel modeling (MLM) will be used to analyze these variables as predictors of CAPS-5 at final session within and between treatment groups.

Exploratory analyses will examine group differences in the number of sessions required to attain significant symptom improvement on the PCL-5 from baseline (Rothbaum et al., 2014) and durability of effects at 1-month follow up. Data from both groups will be harnessed to explore the development of patient-specific algorithms predicting optimal engagement during IVE.

**Data Management and Capture.** We plan to use REDCap (Research Electronic Data Capture) for data capture and management for self-report surveys and clinical interviews. REDCap is a software toolset and workflow methodology for electronic collection and management of research and clinical trial data. REDCap provides secure, web-based flexible applications, including real time validation rules with automated data type and range checks at the time of entry. Exports are made available for several statistical packages including SPSS, SAS, SATA, R and Microsoft Excel. The system allows the research team to create and engage respondents using a variety of notification methods.

REDCap data dictionaries can be distributed for reuse at multiple institutions. The underlying database is hosted in a secure data center at MUSC/VA, a secure environment for data systems and servers on campus, and includes redundancy, failover capability, backups and extensive security checks. The system has several layers of protection including, user/group account management, "Data Access Groups" which allow data to be entered by multiple groups in one database with segmented user rights for entered data, audit trails for all changes, queries and reports, and Secure Sockets Layer (SSL) encryption. Data that will be collected during IVEs (i.e., physiological data, self-reported SUDs, and video-recorded behavioral observation data), will be stored on Zeriscope's secure cloud-based system, which is HIPAA-compliant and designed to rapidly store quantitative and qualitative data from IVEs. The database will be secure and backed up daily.

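### Covariates for the Hypothesis 2 models are chosen by their association with the outcome measures, with no list, threshold or screening model; they should be fixed in advance

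*Combined protocol and SAP*

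**What the plan says.** Section 11.0 (Data Management), under General Statistical Analyses, first says that "Baseline clinical and demographic characteristics will be collected" and compared between groups. It then gives the selection rule: "Baseline characteristics that are associated with the primary outcome measures will be included as covariates in subsequent analyses". It does not list the candidate characteristics, set a threshold for association, or say whether treatment arm is in the screening model. It also does not say whether the association is judged in this trial or taken from earlier work.

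For Hypothesis 2 the same section says that "independent generalized linear mixed effects models will be used to examine PCL-5 and CAPS-5 scores at final session by group", and "Models will be adjusted, respectively, for baseline PCL-5 and CAPS-5". Those baseline scores are the only covariates fixed by name. Randomization is stratified by baseline CAPS-5, but the PCL-5 model is not said to adjust for it.

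On error control the section says "For all analyses, alpha will be set at 0.05", and its power statement is "for treatment outcome at a probability level of 0.05 for a two-tailed test". Section 13.0 adds: "We will also estimate the effect sizes of interest and provide 95% confidence intervals".

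The pool of candidates can be read from "Table 1. Assessment Instruments and Timeline" in section 10.0. Apart from consent, CAPS-5 and PCL-5, 11 instruments are marked at baseline: demographics, MINI, LEC, C-SSRS, BDI-II, two race-related trauma scales, DTS, PTCI, the COVID-19 survey and the TSR.

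**The concern.** Adjusting for prognostic baseline variables is good practice. The difficulty is choosing them by looking at the outcome they will be used to model, in a sample with about 8 controls. Two mechanisms can follow, depending on how the screen is run.

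- **Arm ignored.** If guided treatment lowers the final score, a covariate that happens to be imbalanced between arms acquires an association with the outcome through the treatment effect. It is then selected more often, and adjusting for it removes part of that effect.
- **Arm in the screen.** This route is closed and the estimate is unbiased. But the variables kept are those that happened to fit the residuals, so the residual variance and the standard error come out too small.

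Hypothesis 2 is the efficacy question, and in a preliminary-efficacy trial the estimate and its interval are what inform the next step. A shrunken estimate or an interval that is too narrow therefore affects the main deliverable.

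**Working it through.** **The plan's own figure.** The document gives no number for the covariate rule. Its one design figure is 80% power for d = 1.02 with N = 32, two-sided 0.05. The two-sample noncentrality is d × √(n₁n₂/(n₁+n₂)).

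- 16 and 16: 1.02 × √8 = 2.885, power 79.7%.
- 24 and 8 (3:1 allocation, equal attrition): 1.02 × √6 = 2.498, power 67.7%.

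So 80% reproduces only with equal arms. That is a separate matter. It is used here only to anchor the reference model below.

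**Inputs from the document.** N = 40; 3:1 allocation; 20% attrition, so 32 completers; d = 1.02; two-sided 0.05; 11 candidate instruments.

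**Assumptions.** Equal attrition (24 and 8); baseline-final correlation 0.5; screening at p<0.05; one variable per instrument; one final score per participant, so that the model reduces to analysis of covariance.

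**Reference model (baseline score only).** In SD units the standard error is √[(1 − 0.5²)(1/24 + 1/8)] = √(0.75 × 0.1667) = 0.354. The noncentrality is 1.02 / 0.354 = 2.88. Simulation agrees: mean SE 0.357, power 0.78, coverage 94.9%.

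**Number of noise variables expected to pass.** 11 × 0.05 = 0.55 per trial; simulation gives 0.54-0.55.

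**Simulation results (several thousand trials per setting).** No candidate is truly prognostic. The correlated candidates have correlation 0.5 with baseline severity and 0.4 with each other. A dash means that the figure is not needed for the argument.

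| Screen | Candidates | Mean estimate (true 1.02) | Power | 95% CI coverage | Type I error |
|---|---|---|---|---|---|
| None, baseline score only | - | 1.02 | 0.78 | 94.9% | about 5% |
| Arm ignored | 11, independent | 0.97-0.98 | 0.74-0.75 | 93.9% | about 5% |
| Arm ignored | 11, correlated | 1.00 | 0.73 | 94.5% | about 5% |
| Arm and baseline in screen | 11, independent | unbiased | - | about 93% | 7.0% |
| Arm and baseline in screen | 11, correlated | - | - | - | 6.3% |
| Arm and baseline in screen | 20, independent | unbiased | - | 90-91% | 8.9% |

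- Arm ignored: shrinkage is 1 − 0.968/1.02 = 5% with independent candidates and 1 − 1.00/1.02 = 2% with correlated ones.
- Arm and baseline in the screen: the mean standard error is about 0.91 of the true sampling SD with 11 independent candidates and 0.88 with 20.
- Arm ignored and no true effect: across the settings tried, Type I error is 4.4-5.3% and coverage 94.7-95.6%, so nothing is lost there.

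**Sensitivity: 11 candidates, two truly prognostic (standardised slope 0.3).**

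- Arm ignored: shrinkage is 7% at 24/8, 6% at 30/10, 9% at d = 0.5, and 9% with screening at p<0.10.
- Arm (without baseline) in the screen: coverage is 92.4% at 24/8 and 93.3% at 30/10.

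**With covariates fixed in advance.** Bias is under 1% of 1.02, coverage is 94.6-95.2% and Type I error is 4.8-4.9%.

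**The case against.** **The wording allows harmless readings.** The sentence does not say that association is judged in this trial's data. It could mean association with the baseline CAPS-5 and PCL-5 scores, or factors already known to be prognostic, and neither would cause the problem. This stands as a limit. But the sentence names no variables and cites no source, so in-trial screening is the natural reading, and the same one-sentence change resolves the ambiguity.

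**A reader might infer that the rule must either bias the effect toward zero or inflate false positives.** The documents do not support that. With arm ignored and no true effect, neither happens, and the plan does not say which screen will be used.

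**The size depends on the candidates.** Many of the instruments are symptom scales likely to correlate with baseline severity, which is already in the model. In that case the bias nearly disappears, although power still drops to about 0.73. Pools of 20 or more need several variables per instrument, which the document does not specify. With 11 independent candidates the bias is about 0.05 SD, against a sampling SD of about 0.36.

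**The fix does not by itself raise power above the rule.** With two prognostic variables among 11, power is 0.78 under baseline-only adjustment and also 0.78 under the arm-ignored rule. It reaches about 0.85 only if exactly those two variables are named in advance. This stands.

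**A reader might also infer that the analyst will try several thresholds and keep the best result.** The plan proposes nothing of the kind, so error rates for that behaviour are not a consequence of the rule.

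**Conclusion.** The point holds at moderate size. On its natural reading the rule gives a worse analysis than a pre-specified covariate set. Which harm arises depends on a screening model that the plan does not state:

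- **Arm ignored, guided treatment effective:** about 2-5% shrinkage, and power about 0.73-0.75 in place of 0.78.
- **Arm ignored, no effect:** no harm to error or coverage.
- **Arm and baseline in the screen:** standard error about 9% too small, coverage about 93%, Type I error about 6-7%; about 8-9% error if the pool is 20.

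These figures rest on 24 against 8 completers, a baseline-final correlation of 0.5, screening at p<0.05, about 11 candidates and, where an effect is present, d = 1.02. None of them shows that adjustment itself is wrong. The fault lies in letting the observed outcome choose the covariates. The named adjustment for each outcome's baseline score is sound and should stay.

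**What to change.** Replace the selection sentence in section 11.0 with a fixed set:

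- Each Hypothesis 2 model adjusts for the baseline value of its own outcome and for baseline CAPS-5, the stratification variable. For the CAPS-5 model these are the same covariate.
- At most one or two further covariates may be added, named in the protocol on prior evidence before outcome data are seen.
- No covariate enters the primary model because of its association with the outcome in this trial. A model with outcome-screened covariates may be reported as a sensitivity analysis, with its threshold and screening model stated.

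The cost is a sentence or two of analysis-plan text, with no change to data collection or patient procedures. The downside is that an unexpectedly strong predictor is used only in the sensitivity analysis. Power beyond that of baseline adjustment is gained only if the named covariates prove truly prognostic.
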